5.1.1 Primary endpoint

The primary efficacy endpoint is response to treatment at Week 24.

Response is defined as:

- An increase in Hb of ≥ 1.5 g/dL from Baseline or Hb normalization at Week 16; AND
- Maintenance of this effect from Week 16 to Week 24; AND
- The absence of PRBC transfusions (between Week 5 and Week 24).

Note: Hb normalization is defined as within normal range (between the defined ULN and LLN), as set by the testing laboratory.

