6.3 Selection of study population

6.3.1 Inclusion criteria

A patient must fulfill the following criteria to be included in the study:

1. Age 18 years or older.
2. Diagnosis of primary CAD on the basis of the presence of all the following criteria at screening:
 - a. Signs of hemolysis with abnormal values for at least 2 of the following hemolytic markers:
 - i. Reduced haptoglobin level (< LLN).
 - ii. Elevated LDH level (> ULN).
 - iii. Elevated indirect bilirubin level (> ULN; > 3 x ULN for patients with Gilbert-Meilengracht syndrome).

iv. Increased ARC (above the ULN).

- b. Monospecific direct antiglobulin test strongly positive for C3d.
- c. Cold agglutinin titer ≥ 64 at 4°C .

3. Hb level ≤ 9 g/dL at screening.
4. An absolute neutrophil count ≥ 1500 cells/mm 3 at screening.
5. Documented results from bone marrow biopsy within 1 year of screening with lymphoproliferative infiltration $\leq 20\%$. Patients who have not received a bone marrow biopsy within 1 year of their screening visit or for whom bone marrow biopsy reports are incomplete or unavailable will be required to receive a bone marrow biopsy to determine eligibility.
6. Body weight ≤ 100 kg.
7. Either have vaccination against *S. pneumoniae*, *N. meningitidis* (Types A, C, W, Y, and B), and *H. influenzae* (Type B) within 2 years prior to screening or agree to receive vaccination during screening as follows:
 - First dose of vaccine against *N. meningitidis* Types A, C, W, and Y at least 2 weeks prior to start of study drug with second dose 2 months later (Study Day 57), and then boosters every 5 years.
 - First dose of the vaccine against *N. meningitidis* Type B at least 2 weeks prior to start of study drug with a second dose after at least 1 month (Study Day 29). First booster dose 1 year later, and then additional booster doses every 2 to 3 years.
 - *S. pneumoniae*: PCV13 and/or PPSV23 as per ACIP guidelines for adults or children with immunocompromising conditions.
 - *H. influenzae* Type B: 1 dose at least 2 weeks prior to start of study drug.

Vaccination is mandatory unless documented evidence exists that patients are nonresponders to vaccination. Vaccinations should be administered following the ACIP recommendations for adults or children with complement deficiencies and/or immunocompromising conditions.

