### **7.3.3 Normalization of markers of hemolysis (LDH, indirect bilirubin and ARC) at Week 24**

For the normalization of markers of hemolysis (LDH, indirect bilirubin and ARC) at Week 24, the number and percentage of patients who achieve normalization will be tabulated by treatment group and compared between treatment groups using an exact CMH test stratified for the criterion used for randomization strata ( $\geq 1/0$  transfusions during the 6-month period prior to randomization). The strategy for handling ICEs will be the same as for the primary endpoint where patients meeting an ICE will be considered not normalized. A parameter is considered to have met the normalization response criteria if the patient has a non-normal result at baseline and then has a lab value for that parameter which is in the normal range post-baseline, as defined in the laboratory data.

If data at Week 24 is missing the patient will be considered not normalized.

A composite strategy for handling of ICEs will be used for these endpoints, if any of the ICEs as listed below occurs, the patient is not considered normalized at Week 24 and will be set to non-responder.

- Withdrawal from treatment or lost to follow-up before end of the double-blind period
- Use of prohibited medications (rituximab alone or in combination, any other complement inhibitor, any other investigational drug and plasma exchange. Phlebotomy/venesection is not included).
- Transfusion from Week 5 to Week 24.

Kaplan-Meier plots will be presented for the time-to-event endpoints of time to first normalization from Baseline to Week 24 for LDH, Hb, indirect bilirubin and ARC for each treatment group at Week 24, and Kaplan-Meier estimates will be provided.

Central laboratory values will be used for the endpoint assessments above except ARC which will be assessed locally.

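### SAP 7.3.3 defines normalization of LDH, indirect bilirubin and ARC without direction and without a rule for Gilbert patients, so a low ARC that rises into range would count as normalized

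*SAP*

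**What the plan says.** SAP 7.3.3 covers normalization of LDH, indirect bilirubin and ARC at Week 24. A marker meets the criterion if the patient "has a non-normal result at baseline and then has a lab value for that parameter which is in the normal range post-baseline", the range being taken "as defined in the laboratory data". The section prints no limits, does not say whether the baseline must be high or low, and does not mention Gilbert syndrome; nor does any other part of the SAP. The proportions are compared by an exact CMH test. The same section provides Kaplan-Meier output for time to first normalization and gives no separate rule for it.

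The protocol lists these endpoints but does not define normalization for them. It does define it for hemoglobin, in Section 5.1.1: "Hb normalization is defined as within normal range (between the defined ULN and LLN), as set by the testing laboratory".

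Protocol 6.3.1, criterion 2a, says when each marker is a sign of hemolysis for entry, and there the direction is explicit:

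- LDH: "Elevated LDH level (> ULN"
- ARC: "Increased ARC (above the ULN"
- Indirect bilirubin: "Elevated indirect bilirubin level (> ULN; > 3 x ULN for patients with Gilbert-Meilengracht syndrome"

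Entry requires "abnormal values for at least 2 of the following hemolytic markers", the fourth being haptoglobin below LLN.

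**The concern.** The endpoint is presented as normalization of markers of hemolysis. For these three markers the protocol recognises hemolysis only in a high value, whereas the SAP rule accepts any abnormal baseline and any return to range. The two can disagree for an individual patient. The clearest case is a low ARC that rises and is then reported as a hemolysis marker that normalized.

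The Gilbert provision is a second gap. The entry criterion expects such patients and sets a separate bilirubin cut-off for them, but the endpoint does not say how they are to be judged.

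At stake is the meaning of a between-group comparison that is still to be run. SAP 1.1 keeps the Part A secondary efficacy analyses after the early stop and drops normalization only beyond Part A. If the rule is settled by the programmer, or after the data are seen, the choice is no longer pre-specified.

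**Working it through.** **Is there a figure to reproduce?** Not for this endpoint. The documents give no assumed normalization rate, power, reference range, Gilbert prevalence or frequency of values below LLN. The sample size in Protocol 8.1 and SAP 2.3 concerns the primary endpoint. Its inflation step reproduces: 54 / 0.95 = 56.8, rounded up to 57.

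**Step 1: what the rule means by normal.** The SAP defers to the laboratory. Where the documents explain a normal range (hemoglobin), it runs from LLN to ULN. A programmer would reasonably code 7.3.3 the same way wherever the laboratory supplies both limits.

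**Step 2: can a low ARC occur at entry?** Yes. Two abnormal markers of four suffice. A patient with haptoglobin below LLN and LDH above ULN satisfies criterion 2a whatever the ARC.

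**Step 3: the two rules side by side.**

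| Case | Baseline | Week 24 | SAP 7.3.3 | Entry sign of hemolysis, baseline → Week 24 |
|---|---|---|---|---|
| ARC, low baseline | < LLN | in range | normalized | absent → absent |
| Any of the three, falling past the range | > ULN | < LLN | not normalized | present → absent |
| Indirect bilirubin, Gilbert patient | 4 x ULN | 2 x ULN | not normalized | present → absent |
| Indirect bilirubin, Gilbert patient | 2 x ULN | in range | normalized | absent → absent |

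The first two rows need a laboratory LLN. For LDH and indirect bilirubin the documents do not show whether one exists.

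**Step 4: the weight of one patient.** With 57 randomized 2:1, the groups are 57 x 2/3 = 38 and 57 x 1/3 = 19. One reclassified patient moves a rate by 1/38 = 2.6 percentage points on pegcetacoplan or 1/19 = 5.3 points on placebo. SAP 1.1 says enrollment ended below target but gives no number, so the actual weight is larger by an amount the documents do not let us compute.

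**Step 5: the effect on the comparison.** This would need the number of patients in each row of the table, by group. None of those counts is in the documents, so neither the size nor the direction of the effect can be derived.

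**The case against.** The best defence is that normalization means a return to the normal range. The protocol uses that meaning for the one parameter it defines, and SAP 7.3.3 follows it. Criterion 2a does a different job: it decides who enters. On that view the documents do not contradict each other, and no longer elevated is simply another endpoint that a reviewer might prefer. The consequences are also limited. The endpoint is outside the hierarchy, the Kaplan-Meier output carries no specified test, and the same markers are analyzed as continuous changes under SAP 7.3.2 without this dichotomy. Out-of-range values are flagged in the laboratory listings.

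Most of this stands. It does not rescue the low-ARC case. A rule that reports a rise in reticulocytes from below LLN as normalization of a hemolysis marker does not measure what the endpoint names. It also leaves the handling of Gilbert patients open.

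Three stronger readings are tempting, and the documents do not support them:

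- *Patients whose hemolysis has resolved are being counted as failures.* The documents do not show that any patient has Gilbert syndrome, a low baseline ARC or a Week 24 value below LLN. A Gilbert patient between ULN and 3 x ULN is not shown to be free of hemolysis, and an ARC below LLN need not mean that hemolysis has resolved.
- *The SAP ignores a protocol threshold.* The 3 x ULN limit is an entry cut-off. Neither document makes it a response threshold.
- *The errors shrink the treatment difference and cost power.* That would follow if equal shares of both groups were misclassified. In a trial this small, low-ARC false successes could fall unevenly either way, and any power figure would rest on normalization rates that the plan does not state.

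**Conclusion.** The point holds as a defect of definition. The direction of change is missing for all three markers; the low-ARC case follows directly from the wording, given a laboratory LLN for ARC. The fall from above ULN to below LLN is conditional on a laboratory lower limit for the marker concerned. For Gilbert patients the defect is a missing rule, not a breach of an existing one.

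Only the secondary normalization and time-to-first-normalization endpoints are touched, together with the exploratory haptoglobin endpoints, for which SAP 7.7 gives no definition of normalization. The primary endpoint, the key secondary endpoints and the sample size are unaffected. If no patient falls into one of the discordant cases, the effect is zero. It is a minor point, worth making because the comparison is still planned and the correction is cheap.

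**What to change.** Replace the sentence in SAP 7.3.3 with a directional rule:

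- For LDH, indirect bilirubin and ARC, normalized means baseline > ULN and Week 24 ≤ ULN.
- For haptoglobin (exploratory), it means baseline < LLN and Week 24 ≥ LLN.
- Time to first normalization of these markers uses the same limits, applied at the first qualifying visit. Hemoglobin keeps its protocol definition.
- Any Week 24 ARC below LLN is listed.

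Before unblinding, state how Gilbert patients are handled for indirect bilirubin, for example by excluding them from that endpoint. The 3 x ULN entry cut-off should not be adopted by default: it would call a fall from 3.1 to 2.9 x ULN normalization.

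The same text should say whether patients whose baseline is not abnormal in the relevant direction stay in the denominator. They cannot meet the rule, and 7.3.3 does not say whether they count as failures in the ITT set.

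The cost is a short SAP edit and a change to the derivation code. One downside is that an ARC that drops below LLN counts as normalized, which is why the listing is needed. Another is that excluding Gilbert patients would reduce the number analyzed for indirect bilirubin.

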### **7.3.4 Number of units of PRBCs transfused from Week 5 to Week 24**

The number of units of PRBCs transfused from Week 5 to Week 24 in each treatment group will be compared using a stratified Wilcoxon rank-sum test (i.e., the Van Elteren test). Patients who withdraw before Week 24 will have the number of units estimated from the duration that they were in the study until withdrawal or initiation of prohibited medication.

The average number of units transfused for the duration where a patient has evaluable data for PRBC transfusions will be used to estimate the total number of transfused units that would have been used through Week 24 had they not withdrawn from the study.

If the number of PRBC is reported in units and mL in the database the mL will be converted to units using the following formula:

$$\text{Number of PRBC units} = \text{Round}(\text{PRBC (mL)} / 300), 1.$$

### **7.3.5 Change from Baseline at Week 24 in SF-12, EQ-5D-5L and the FACIT-F subscale score of the FACT-An scale.**

The change from Baseline at Week 24 in SF-12, EQ-5D-5L and FACIT-F subscale score of the FACT-An scale will be analyzed using MMRM with the fixed effects of treatment, strata, visit, visit-by-treatment interaction and the respective baseline level as covariate, using an unstructured covariance matrix and the Kenward-Roger method for calculating the degrees of freedom. Should the model fail to converge with an unstructured covariance matrix, other covariance structures such as autoregressive (1) will be attempted first followed by compound symmetry after that if needed. The difference between treatment groups will be estimated, along with its 95% CI and p-value.

The ICEs and their associated strategies to handle them, will be the same as for the key secondary endpoint Change from Baseline to Week 24 in Hb level. Additional (descriptive only) summary tables of change from baseline irrespective of ICEs will be created for SF-12, EQ-5D-5L and the FACIT-F subscale score of the FACT-An scale.

Summary statistics by treatment groups will be presented at each assessment visit during the 24-week double-blind treatment period.

SF-12 summary will show two separate composite scores (MCS and PCS) as provided by QualityMetrics.

For EQ-5D-5L, the visual analogue score and each of the 5 dimensions will be summarized.

For the FACIT-F score, the total score will be summarized as well as the percentage of patients with at least a 4-point improvement from Baseline at Week 24 and Week 48.

The FACT-An scores that will be summarized are the total score, physical subscore, social subscore, emotional subscore, functional subscore, and anemia subscore.

Reference documents for quality of life scores may be used as needed. These include the FACT-An Scoring Guidelines, FACIT Fatigue Scale (Version 4) guidelines, and the EQ-5D-5L (Version 3.0 SEP2019) User Guide.

## 7.4 SECONDARY EFFICACY ENDPOINT ANALYSIS FOR PART B

All Part B secondary efficacy analyses will be analyzed with the ITT set, and data presentations will be by visit and by randomized treatment group in Part A as well as combined.

The change from Baseline at Week 48 in Hb, LDH, haptoglobin level, indirect bilirubin, ARC and D-dimer will be analyzed using descriptive statistics.

For the endpoint regarding the normalization of markers of hemolysis (LDH, indirect bilirubin and ARC) at Week 48, the number and percentage of patients who respond will be tabulated in frequency tables by randomized treatment group in Part A as well as combined. All data will be used as collected (no ICEs will be considered) and no imputations will be done.

Durability of response is the time until response is lost; response is lost at the first time point when the average change from baseline in Hb is < 1.5 g/dL (the average of all time points starting from Week 24), or the patient receives a transfusion, or the patient discontinues treatment or the study or the patient receives prohibited medication. Durability of response will be analyzed as a time to event variable with Kaplan-Meier statistics provided. Only patients randomized to pegcetacoplan in Part A who achieved the primary endpoint at Week 24 will be included in this analysis. The time to event will be defined as the time the patient achieved the primary endpoint at Week 24 until the earliest time durability of response (as defined above) is lost. Due to the termination of the study, durability of response will not be included in the analysis.

The change from Baseline at Week 48 in FACT-An, SF-12, EQ-5D-5L and FACIT-F subscale score of the FACT-An scale will be analyzed using descriptive statistics.

All data will be used as collected (no ICEs will be considered) and no imputations will be done.

## 7.5 TERTIARY EFFICACY ENDPOINT ANALYSIS FOR PART C

All tertiary efficacy analyses will be analyzed with the ITT set and data presentations will be by visit and by randomized treatment group in Part A as well as combined.

The change from Baseline at Week 96 in Hb, LDH, haptoglobin, indirect bilirubin, ARC and D-dimer will be analyzed using descriptive statistics.

For the endpoint regarding the normalization of markers of hemolysis (LDH, indirect bilirubin and ARC), at Week 96, the number and percentage of patients who respond will be tabulated in frequency tables by randomized treatment group in Part A as well as combined.

The change from Baseline at Week 96 in FACT-An, SF-12, EQ-5D-5L and FACIT-F subscale score of the FACT-An scale will be analyzed using descriptive statistics.

All data will be used as collected (no ICES will be considered) and no imputations will be done.

## 7.6 SAFETY ENDPOINT ANALYSIS

All safety analyses will be carried out descriptively on the safety set and presented by randomization sequence. For each output summary, all data will be presented as it becomes available. For example, data for Part A will be presented when Part A is reported. When Part B data are available, all cumulative data from Parts A and B will be reported together. When Part C data are available, all cumulative data from Parts A, B, and C will be reported.

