8.3.5 Analysis of safety and tolerability data

All safety analyses will be carried out descriptively on the safety set, consisting of all patients who received at least 1 dose of IMP.

In general, the evaluation of safety and tolerability is carried out separately for the double-blind placebo-controlled period and the open-label period. Other analyses are detailed in the SAP.

Pretreatment AEs are those occurring between ICF signature and the first IMP administration. TEAEs are defined as those AEs that develop or worsen after the first dose of IMP and up to 8 weeks after the last dose of study medication.

All AEs will be coded using the MedDRA. Pretreatment AEs will be summarized by SOC and PT. TEAEs will be summarized by SOC, PT, treatment group for number of patients and proportion reporting the event. A similar summary will be produced for SAEs, AEs leading to premature discontinuation of IMP and AEs related to the IMP. The intensity of AEs and the relationship to the IMP will be summarized for each SOC and PT by treatment group.

AEs leading to IMP discontinuation will be summarized by frequency tables.

The results of laboratory assessments, anti-pegcetacoplan peptide/anti-PEG Ab assessments, vital signs and ECGs will be summarized by treatment group using appropriate descriptive statistics.

The AE summaries will be presented across all patients. All AEs will be listed by patient, along with information regarding onset, duration, relationship to IMP, severity, action taken with IMP, treatment of event and outcome.

Changes from Baseline in clinical laboratory test results will be summarized using descriptive statistics. Baseline will be taken as the measurement closest, but prior, to the first dose of IMP. Out-of-range values will be flagged in data listings.

Laboratory data and vital signs will be graded for severity using CTCAE v 5.0 and all Grade ≥ 3 results will be considered clinically meaningful.

Changes in physical examinations will be described in a data listing.

Safety data will include all data up to Week 24 for reporting Part A, all data up to Week 48 for reporting Part B, and all data for reporting Part C.

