### 7.6.1 Adverse events

Pretreatment AEs are those occurring between ICF signature and the first IMP administration. Treatment-emergent Adverse Events (TEAEs) are defined as those AEs that start on or after the first dose of IMP and up to 8 weeks after the last dose of study medication.

An overall summary table will summarize the following information by treatment group.

- Treatment-emergent adverse events (TEAEs)
- Serious adverse events (SAEs)
- Non-serious adverse events
- TEAEs leading to premature discontinuation of IMP.
- TEAEs leading to death
- Device related TEAEs
- TEAEs by severity

Separate tables will be presented with the following summaries:

- TEAEs of special interest will be summarized: infections (defined as any AE with SOC “Infections and Infestations”), and injection site reactions (from eCRF)
- Pretreatment AEs by PT
- TEAEs by SOC and PT, including incidence rates.
- TEAEs by PT, including incidence rates.
- Non-serious TEAEs by SOC and PT, including incidence rates.
- Non-serious TEAEs PT, including incidence rates.
- Treatment-emergent SAEs PT, including incidence rates.
- TEAEs leading to premature discontinuation of IMP by PT, including incidence rates.
- TEAEs related to the IMP by PT, including incidence rates.
- Treatment-emergent SAEs related to the IMP by PT, including incidence rates.
- TEAEs by severity (mild/moderate/severe) and PT, including incidence rates.
- TEAEs that were injection site reactions, by PT.

The time at risk per patient is defined as time from first dose of study drug to last dose of study drug + 56 days (treatment-emergent), or death, if earlier, for those patients without a respective TEAE. For patients with an TEAE, time at risk is defined as the time from first dose of study drug to TEAE start date. Exposure adjusted incidence rates will be calculated as (number of patients with AE/total person-years at risk)\*100.

All AE data will be presented in a listing and include at least onset date, duration, relationship to IMP, severity, action taken with IMP, treatment of event, and outcome.

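### Cumulative AE rates for patients who switch from placebo combine placebo and pegcetacoplan time on one first-event clock, and no SAP table gives a pegcetacoplan rate that includes them

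*SAP*

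**What the plan says.** **Grouping and cumulation.** SAP 7.6: "All safety analyses will be carried out descriptively on the safety set and presented by randomization sequence". Part A comes first on its own: "data for Part A will be presented when Part A is reported". Then: "When Part B data are available, all cumulative data from Parts A and B will be reported together". The same is done for Parts A to C once Part C data exist.

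**Clock.** SAP 7.6.1 gives a patient without the event in question the "time from first dose of study drug to last dose of study drug + 56 days", cut short by death. With an event: "For patients with an TEAE, time at risk is defined as the time from first dose of study drug to TEAE start date". The rate is "number of patients with AE/total person-years at risk", times 100. Nothing restarts at Week 24.

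**Switch.** Protocol 6.1.2 counts placebo as IMP. Protocol 6.1.3 makes all Part A completers eligible for open-label pegcetacoplan, and 6.4.9.1 has every patient on it after Week 24. For a switcher, both the treatment-emergent window and the clock therefore begin with the first placebo infusion.

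**Periods.** Protocol 8.3.5 says, as a general rule, that "the evaluation of safety and tolerability is carried out separately for the double-blind placebo-controlled period and the open-label period". The same section also sets cumulative data cuts at Week 48 and at the end of the study. SAP 11.1 lets the SAP prevail where the two differ.

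**Column labels.** SAP 7.6 uses randomization sequence, 7.6.1 treatment group, and 4.2 treatment received. These do not describe the same column for a switcher.

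**Early termination.** SAP 1.1 leaves the safety summaries as planned, drops the specific Part B and C tables, and allows treatment until 10 July 2024 after enrollment stopped on 10 January 2024.

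**The concern.** Assessing the safety and tolerability of pegcetacoplan is a stated secondary objective. Switchers are newly exposed patients, and Protocol 4.3 names a potential increased risk of infection with encapsulated bacteria. SAP 7.6.1 treats infections as events of special interest and plans incidence rates by SOC and by PT.

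As written, two things happen in the placebo-first column of the cumulative tables. Placebo weeks enter the denominator, and placebo events the numerator, of a rate that also contains pegcetacoplan experience. And because each patient counts once per term, an event on placebo closes that patient's clock for the term before the first pegcetacoplan dose. Unless the two rates happen to be equal, the column estimates neither treatment's rate. No table described in the SAP supplies the pegcetacoplan rate that is missing.

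**Working it through.** The plan gives no AE rate, so there is no stated figure to reproduce. The check applies the SAP 7.6.1 clock to assumed rates.

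**Inputs from the documents:** 24 weeks of Part A, 24 of Part B, up to 48 of Part C, and a 56-day (8-week) tail. **Assumed:** a constant rate within each treatment period and complete follow-up.

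Let h0 and h1 be the placebo and pegcetacoplan rates per year, T0 = 24/52.18 = 0.460 years, and T1 the pegcetacoplan time including any tail.

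- Share leaving the risk set before the switch: 1 − exp(−h0·T0)
- Expected patients with an event: 1 − exp(−h0·T0 − h1·T1)
- Expected person-years: [1 − exp(−h0·T0)]/h0 + exp(−h0·T0)·[1 − exp(−h1·T1)]/h1
- Tabulated rate: 100 × events / person-years

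Worked case, h0 = 0.5, h1 = 1, T1 = 24 weeks:

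- Placebo period: 0.2055 events in 0.2055/0.5 = 0.4109 person-years.
- Pegcetacoplan period: 0.7945 × 0.3687 = 0.2929 events in 0.2929 person-years.
- Rate: 100 × 0.4984/0.7038 = 70.8, against a pegcetacoplan rate of 100.

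| Assumed placebo / pegcetacoplan rate per 100 PY | Leave before switch | Parts A+B, no tail (24+24 wk) | Parts A+B with tail (24+32 wk) | Parts A to C with tail (24+80 wk) |
|---|---|---|---|---|
| 5 / 10 | 2.3% | 7.5 | 7.8 | 8.8 |
| 10 / 20 | 4.5% | 14.8 | 15.5 | 17.4 |
| 50 / 50 | 20.5% | 50.0 | 50.0 | 50.0 |
| 50 / 100 | 20.5% | 70.8 | 73.5 | 80.1 |
| 100 / 200 | 36.9% | 134.0 | 137.7 | 144.9 |
| 100 / 50 | 36.9% | 79.3 | 76.3 | 67.6 |

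The column is pulled toward the placebo rate, whichever rate is higher, and is unbiased when they are equal. For uncommon terms few patients leave early, but dilution by placebo time stays.

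**Placebo share of an event-free switcher's clock.** End of Part B with tail: 24/56 = 43%. End of Part C with tail: 24/104 = 23%.

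**Under early termination.** From 10 January to 10 July 2024 is 182 days, or 26 weeks. A patient randomized at the end of enrollment who completes Part A has at most 26 − 24 = 2 weeks of pegcetacoplan dosing. The clock is then 24 + 2 + 8 = 34 weeks, and placebo is 24/34 = 71% of it. With rates 50/100 and T1 = 10 weeks, the formula gives 62.6.

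**The case against.** **The SAP does not clearly reverse the protocol.** A reader might infer a direct contradiction. Protocol 8.3.5 words the separate evaluation as a general rule and itself prescribes cumulative cuts. The SAP repeats the cumulation and is silent on the separation, and reporting parts together does not rule out period columns. This stands: the SAP fails to carry the separate evaluation through, but does not expressly abandon it.

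**The layout is not final.** Three labels compete for the column, and SAP 10.1 leaves table specifications until after the SAP. That is fair, but the clock rule is explicit in 7.6.1, and no label or later document supplied here assigns events by treatment at onset.

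**Much safety information is untouched.** It is tempting to say that pegcetacoplan safety in switchers cannot be read at all. The documents do not support that. Part A is reported alone, so the randomized comparison is intact. The pegcetacoplan-first column has only one treatment. SAP 5.2.3 keeps by-visit data within Part A or the open-label parts and splits Week 24 at the first open-label dose. AE listings show onset date and relationship. What stays lost is a tabulated rate: subtracting Part A from a cumulative table recovers only first events in patients who were event-free at the switch.

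**The size may be small.** With equal rates there is no bias, and at placebo rates of 5 to 10 per 100 person-years only about 2 to 5% of switchers leave before switching. Both points stand. The figures for Parts A to C also assume the full planned length, which early termination cuts short for late-randomized patients. The number actually randomized is not in the documents.

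**Conclusion.** The point holds for the exposure-adjusted AE rates in the placebo-first column of the cumulative Part A+B and A to C output. Followed as written, those rates blend two treatments, drop patients with a placebo-period event of a term before they reach pegcetacoplan, and leave the switchers without a pegcetacoplan rate. The conflicting column labels add to the problem.

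The size rests on assumed constant rates. It is zero if the rates are equal. At 50 and 100 per 100 person-years the column shows about 71 to 80 instead of 100, with about 20% of switchers leaving first. Placebo can be up to about 71% of a late-randomized switcher's clock under the early termination. A reader might take the doubling scenarios as a forecast that a signal will be hidden. They only illustrate the mechanism, and if pegcetacoplan lowered a rate the bias would run upward. Safety analysis here is descriptive, so no hypothesis test is affected. The change should be made because the mixed rate bears on a stated safety objective and is cheap to avoid.

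**What to change.** In SAP 7.6 and 7.6.1, for the cumulative tables:

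- **(a)** Assign each TEAE to the treatment being taken at its onset, and end placebo time at risk at the first open-label dose.
- **(b)** Add an any-pegcetacoplan column whose first-event flag and time at risk start at the first pegcetacoplan dose: Day 1 for patients randomized to it, the first open-label dose for switchers.
- **(c)** Keep the Part A table by treatment arm unchanged, and use one column definition consistently across 4.2, 7.6 and 7.6.1.

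This also carries through the separate evaluation in Protocol 8.3.5. It needs SAP wording, one derived date (SAP 5.2.3 already relies on the start of open-label dosing) and one more column. No new data are collected. The downside is slightly longer AE tables.
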